4.8. Population

Patients of both sexes and any age with cancer being treated and followed up at Pio XII Foundation hospitals who have developed malignant ureteral obstruction requiring percutaneous nephrostomy as part of their treatment from January 2013 to June 2020 at the Jales Cancer Hospital and from January 2014 to June 2020 at the Barretos Cancer Hospital.

4.9. Sample size calculation

The retrospective cohort will be made up of 372 consecutive, non-probabilistic patients for convenience, according to data collected from the institution's hospital

system (SisOnco). These patients will be studied according to the procedures performed, divided into first catheter passage and catheter change.

In the first pass of the percutaneous nephrostomy catheter group, 372 procedures were carried out at the Barretos and Jales Cancer Hospitals. In the catheter change group, 358 procedures were carried out in the stipulated period. Totaling 730 procedures carried out at the two hospitals between January 2013 and June 2020.

4.10. Study Conduct, Measurements and Methodology

One of the main aims of this study is to assess the rates of urinary tract infection related to the percutaneous nephrostomy procedure in cancer patients. At the first catheter change, groups will be assessed according to whether or not antibiotic prophylaxis was used. At subsequent catheter changes, groups will be assessed according to the type of antibiotic prophylaxis used (uroculture-guided *versus* empirical).

Patients eligible for the study will be identified when, during follow-up at the Pio XII Foundation, there was an indication for the image-guided percutaneous nephrostomy procedure after due assessment by the urology and/or interventional radiology teams.

The medical records of patients who underwent the procedure from January 2013 to June 2020 at the Jales Cancer Hospital and from January 2014 to June 2020 at the Barretos Cancer Hospital will be retrospectively reviewed using the database provided by the institution itself (SisOnco).

4.10.1. Definitions

In order to carry out this study, it is necessary to establish some concepts, some of which are not yet standardized in the medical literature:

- **Urinary tract colonization:** occurs when there is a positive uroculture result (presence of infectious agents such as bacteria or fungi) in the absence of clinical signs suggestive of infection. In these cases, antibiotic treatment is not necessary (45).
- **Urinary tract infection:** occurs when there are signs and symptoms suggestive of local infection, such as cystitis (bladder infection or lower urinary tract infection) or pyelonephritis (kidney infection or upper urinary tract infection) associated with a positive uroculture result, requiring treatment with antibiotics ^{3, 19, (46)}.

- **Urinary tract infection related to the percutaneous nephrostomy procedure:** when the urinary tract infection occurs shortly after the procedure has been carried out, in this case, percutaneous nephrostomy (first pass or catheter changes).
- **Urinary tract infection related to the nephrostomy catheter:** when the urinary tract infection occurs at another time unrelated to the procedure and in the presence of the nephrostomy catheter and in the absence of another focus justifying the infection.

4.10.2. First pass procedure

This group will be made up of patients who have undergone percutaneous nephrostomy for urinary tract clearance and we will study whether or not antibiotic prophylaxis was recorded in the medical records to be reviewed at these hospitals.

The following laboratory tests will be considered: serum creatinine and urea levels, urine samples for tests such as urine summary (or type I urine) and uroculture with antibiogram.

The proportion of urinary tract infections that developed within 7 days of the procedure will be studied. A procedure-related urinary tract infection is considered to be any report in the medical record of clinical signs and symptoms associated with uroculture results (see definition in item 4.10.4.) and the location of the respective treatment will be documented: outpatient, inpatient or intensive care unit (ICU).

It will be documented whether there is evidence reported in medical records of urinary tract infections or the presence of bladder fistulas prior to the procedure.

4.10.3. Procedure for changing the catheter

Catheter changes take place electively approximately every 90 days after the previous procedure (first pass or previous catheter change), scheduled during outpatient follow-up. However, this change can happen earlier than planned due to situations such as catheter obstruction and migration, or even catheter-related urinary tract infection.

This group will be made up of patients undergoing percutaneous nephrostomy catheter exchange and will study the use of empirical or targeted antibiotic prophylaxis documented in medical records to be reviewed at the two hospitals.

The Jales Cancer Hospital will study targeted antibiotic prophylaxis, which consists of collecting the following laboratory tests around 7 days before the procedure

to change the nephrostomy catheter(s) to guide the antibiotic to be used for prophylaxis: serum creatinine and urea levels, urine samples for tests such as urine summary (or type I urine) and uroculture with antibiogram. If the tests are not carried out prior to the procedure or if the uroculture does not show a specific bacterial agent, the procedure will be studied according to empirical antibiotic prophylaxis.

The Hospital de Câncer de Barretos will study the empirical antibiotic prophylaxis carried out according to daily clinical practice, recorded in the medical records to be reviewed of patients undergoing percutaneous nephrostomy catheter exchange.

The proportion of urinary tract infections that developed within 7 days of the procedure will be studied. A procedure-related urinary tract infection is considered to be any report in the medical record of clinical signs and symptoms associated with uroculture results (see definition in item 4.10.4.) and the location of the respective treatment will be documented: outpatient, inpatient or intensive care unit (ICU).

It will be documented whether there is evidence reported in medical records of urinary tract infections or the presence of bladder fistulas prior to the procedure.

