1.4.1. Minor complications

There are reports of a 3% to 28% prevalence of minor complications ^{23, 24}, with spontaneously resolving hematuria accounting for 13.2% to 18.9% ^{22(,)(23)(,)(25)}; pain occurs in 25% of cases ²² and catheter migration ranges from 12% to 17% ^{10) .. (22)}

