4.12. Statistical Analysis

The data will initially be tabulated in an electronic spreadsheet in REDCap and for the statistical analysis, only the research team's statistician will download the data into the statistical program (SPSS). The study population will be characterized using descriptive statistics, using the mean, standard deviation, minimum, maximum and quartiles for quantitative variables and frequency tables for qualitative variables.

The database will be made up of patient information and procedure information, but with a unique identifier for each patient, allowing information to be linked between them.

For the purposes of this study, nephrostomy procedures will be considered independent. The procedures will be separated into first pass and catheter changes. In the first passage, procedures with antibiotic prophylaxis and without antibiotic prophylaxis will be studied. In catheter changes, procedures with empirical antibiotic prophylaxis and with targeted antibiotic prophylaxis will be studied. The types of procedures and the other characteristics of the procedures will be associated with the occurrence of urinary tract infection using the Chi-square test or Fisher's exact test, depending on the expected values in the contingency table. The multiple analysis will be carried out using Logistic Regression with multiple variables. To this end, only the variables with a p-value of less than 0.20 in the univariate analysis will be selected for the model.

The significance level will be 5%, two-sided, for all statistical analyses, which will be carried out using the SPSS v21 program.

Part II - Systematic Review and Meta-Analysis

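### The targeted-versus-empirical comparison at catheter changes pools scheduled and unplanned changes, so it is confounded by the reason for the change, and the planned adjustment does not reliably control this

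*Protocol*

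**What the plan says.** Protocol section 4.10.3 describes two kinds of change. The routine one is elective: "Catheter changes take place electively approximately every 90 days after the previous procedure (first pass or previous catheter change), scheduled during outpatient follow-up". The other is early: "this change can happen earlier than planned due to situations such as catheter obstruction and migration, or even catheter-related urinary tract infection".

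The same section sets the arms. Targeted prophylaxis, studied at Jales, consists of "collecting the following laboratory tests around 7 days before the procedure" and choosing the antibiotic from the result. There is a fallback: "If the tests are not carried out prior to the procedure or if the uroculture does not show a specific bacterial agent", then "the procedure will be studied according to empirical antibiotic prophylaxis". Barretos "will study the empirical antibiotic prophylaxis carried out according to daily clinical practice".

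The analysis in section 4.12 does not separate the two kinds of change: "In catheter changes, procedures with empirical antibiotic prophylaxis and with targeted antibiotic prophylaxis will be studied". Section 4.12 and the SAP's statistical analysis section both use logistic regression with variables chosen by a univariate p-value below 0.20. Scheduled status is not a stratum, a restriction or a required covariate.

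The variable lists (protocol section 4.10.5 and the SAP) include period of catheter use, catheter mobility and obstruction, but not the reason for a change. The collection form (Appendix II) is not in the public text, so whether it records the reason cannot be checked.

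**The concern.** Whether culture-guided prophylaxis beats empirical prophylaxis at changes is the second of the two guiding questions at the end of section 1.5.2.3. A change forced by a blocked or displaced catheter will less often have a culture from about a week before than one booked in clinic. By the plan's own allocation rule, such a change then counts as empirical at Jales, and it is empirical at Barretos in any case. The arms can therefore differ at the moment of the change in whether the system was obstructed, displaced or becoming infected. Section 1.5.1 links catheter fouling and dysfunction to clinical infection, so a higher risk at unplanned changes is plausible, although no figure is given.

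There is also a narrower worry about reverse causation. An infection that prompted an early change, but was neither diagnosed nor treated by then, could be diagnosed within 7 days and counted as procedure-related, mostly in the empirical arm.

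**Working it through.** **Plan figures.** Section 4.9 gives 372 first passes and 358 changes: 372 + 358 = 730, as stated. It does not split the 358 by arm, hospital or scheduled status. The only effect data are from the institution's own earlier cohort (section 1.5.2.3), with infection at changes of 14.8% (empirical) and 6.4% (targeted), a ratio of 6.4/14.8 = 0.43. Counts that fit its three percentages are 3/14 (no prophylaxis), 4/27 and 3/47. The exact test on these gives p = 0.146, matching the protocol.

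**Path 1: unplanned changes in the empirical arm.** Let r be the risk at scheduled changes, u the unplanned share of the empirical arm, and k the risk ratio of unplanned to scheduled. Assume no true effect and no unplanned changes in the targeted arm. Then:

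- empirical risk = r × [(1 − u) + u × k]
- apparent risk ratio, targeted/empirical = 1 / [1 + u × (k − 1)], which does not depend on r

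The documents give neither u nor k. I take u from 12% to 30% and k as 2 or 3. The 12% and 17% are the migration rates cited in section 1.4.1, used only as placeholders, since they are complication rates and not shares of changes. With r = 10%, also assumed:

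| u | k = 2: empirical risk, ratio | k = 3: empirical risk, ratio |
|---|---|---|
| 12% | 11.2%, 0.89 | 12.4%, 0.81 |
| 17% | 11.7%, 0.85 | 13.4%, 0.75 |
| 30% | 13.0%, 0.77 | 16.0%, 0.63 |

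**Could this path alone produce the earlier cohort's gap?** The k needed is [14.8/6.4 − (1 − u)] / u. That is 11.9 at u = 12%, 8.7 at 17% and 5.4 at 30%.

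**Path 2: culture-negative changes in the empirical arm.** The fallback also moves changes whose culture shows no specific agent, which leaves the targeted arm culture-positive. Let g be the culture-negative share of the empirical arm and h their relative risk. The apparent ratio becomes 1 / [u × k + g × h + (1 − u − g)].

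- u = 20%, k = 2, g = 30%, h = 0.5: 1/1.05 = 0.95
- u = 20%, k = 2, g = 50%, h = 0.5: 1/0.95 = 1.05
- u = 20%, k = 2, g = 50%, h = 0.3: 1/0.85 = 1.18

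Over assumed ranges u 10–30%, k 1.5–3, g 10–50% and h 0.3–1.0, the ratio runs from 0.63 to 1.43.

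**Would the p < 0.20 screen pick up scheduled status if it were coded?** I simulated 358 independent changes with 10% risk at scheduled and 20% at unplanned changes. The indicator fails the screen in about 30%, 22% and 12% of data sets when unplanned changes are 12%, 17% and 30% of all 358. A doubling of risk can thus be left out of the model.

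**The case against.** The strongest counter-argument concerns direction. A reader might infer that guided prophylaxis will look better than it is. The documents do not support that. The fallback that collects untested changes in the empirical arm also collects culture-negative ones there. Section 1.5.2 lists bacteriuria among the high-risk features, and section 4.10.4 requires a positive culture for the outcome. Both push against targeted prophylaxis, and only the net matters. Comparing within Jales does not settle the sign, because its culture-negative changes sit in the same empirical group. This objection stands.

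A reader might also infer that only scheduled changes can receive targeted prophylaxis. Section 4.10.3 does not bar an early change with a recent culture, so what is supported is that unplanned changes are less likely to be targeted.

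Reverse causation is partly handled. Section 4.7 excludes changes made under antibiotic treatment for a urinary infection, and section 4.10.4 classes infections diagnosed between changes as catheter-related. What is left is infection both undiagnosed and untreated at the change, a group that the documents do not size.

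Relevant data are planned: prior urinary infection (section 4.10.3), period of use, mobility and obstruction (section 4.10.5), and whether the catheter was changed when an infection occurred (section 3.2). These could enter the regression. But entry depends on the screen, and mobility and obstruction are listed as complications, not as the trigger for the change. This lessens the problem without removing it.

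**Conclusion.** The reason for the change is a real confounder of the targeted-versus-empirical comparison, and the plan does not reliably control it. Taken alone, and if unplanned changes do carry higher risk, it favours targeted prophylaxis, with an apparent risk ratio of 0.89 to 0.63 under no true effect. That range rests on assumed unplanned shares (12% to 30% of the empirical arm), assumed risk ratios (2 to 3) and no unplanned changes in the targeted arm. It illustrates the size and does not estimate it.

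The net direction is unknown once culture result and hospital are considered. Nor should the earlier cohort's 0.43 be read as a product of this path, since that would need a risk ratio of at least 5.4 over these shares. The point deserves correction because it bears on one of the study's two guiding questions and the remedy is cheap. It does not by itself invalidate the comparison.

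**What to change.** 1. Code each change as scheduled or unplanned, with the reason (obstruction, migration, suspected infection, other), from the records under review, helped by the period-of-use, obstruction and mobility fields.
2. Force that indicator into the logistic regression for changes whatever its univariate p-value, together with hospital.
3. Specify a sensitivity analysis restricted to scheduled changes, with unplanned changes reported as a separate stratum.
4. In a further sensitivity analysis, flag infections already suspected and recorded as the trigger for the change. Do not drop every infection with any earlier sign: low back pain and cloudy urine are among the listed signs, and genuine post-procedure infections could be lost.

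**Cost.** One extra coded field and one or two model terms. At the 11.4% rate that section 1.5.2.3 reports for changes, 358 changes would give about 41 infections, so the model must stay small. Because Barretos is studied as empirical only, a hospital term means that the arm effect is estimated essentially within Jales, which should be stated. The scheduled-only analysis loses precision. That matters because power for 14.8% against 6.4% with all 358 changes treated as independent is only about 46% to 74% if 20% to 50% are targeted (assumed splits). This is why scheduled-only is proposed as a sensitivity analysis and not as the sole primary set. None of this removes the culture-result imbalance, which has to be reported alongside. The SAP is written in the past tense, so if the analysis has already been run, the additions should be labelled post hoc.

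### At catheter changes, targeted prophylaxis is placed at one hospital and no hospital term or stratification is planned, so the targeted-versus-empirical comparison does not separate prophylaxis type from hospital

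*Protocol*

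**What the plan says.** Protocol section 4.10.3 allots prophylaxis type at catheter changes by hospital. For one site it says "The Jales Cancer Hospital will study targeted antibiotic prophylaxis"; the other, Barretos, "will study the empirical antibiotic prophylaxis carried out according to daily clinical practice, recorded in the medical records". Between these two statements is a fallback rule for Jales. It covers changes with no prior tests, and also says "if the uroculture does not show a specific bacterial agent, the procedure will be studied according to empirical antibiotic prophylaxis". As written, the targeted group is Jales only, and the empirical group is Barretos plus the Jales fallback changes.

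Section 4.8 sets the periods: "from January 2013 to June 2020 at the Jales Cancer Hospital and from January 2014 to June 2020 at the Barretos Cancer Hospital". Section 4.9 gives the total but no split by hospital or prophylaxis type: "In the catheter change group, 358 procedures were carried out in the stipulated period".

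The variable lists in protocol section 4.10.5 and in the SAP name neither hospital nor procedure date. Section 4.10.5 refers to Appendix II for the full instrument, which is not in the text available. Protocol section 4.12 and the SAP analysis section plan chi-square or Fisher tests and a multiple logistic regression. Variables enter the regression only if their univariate p-value is below 0.20. Neither section mentions a hospital term, stratification by hospital or a within-hospital contrast.

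**The concern.** Whether culture-guided prophylaxis does better than empirical prophylaxis at catheter changes is one of the two questions that the protocol's introduction says guide the project. If the targeted group is one hospital and the empirical group is largely the other, any difference between the hospitals in infection risk or in how infection is detected enters the comparison.

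Detection matters here because section 4.10.4 defines infection from charted signs plus a positive culture, so culture ordering and completeness of records partly decide who counts as a case. Section 4.10.3 describes cultures about 7 days before a change at Jales and daily practice at Barretos. Case mix, operators and local resistance could also differ; the documents do not quantify this.

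At stake is whether a significant result could be attributed to uroculture guidance. The first-pass comparison (prophylaxis or none) is not allotted by hospital and is outside this point.

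**Working it through.** **Figures that can be reproduced.** Section 4.9: 372 first passes + 358 changes = 730, as stated. This is a count, not a power-based sample size. The SAP names the power software but gives no power, effect or group sizes.

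**Calendar overlap.** Jales: 7 × 12 + 6 = 90 months. Barretos: 6 × 12 + 6 = 78 months, all inside the Jales window. 78/90 = 87%. The periods differ only by 2013 at Jales.

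**How far a hospital difference passes into the estimate.** Assumptions, none of them a planned figure:
- prophylaxis has no effect;
- infection is 6.4% at Jales and 14.8% at Barretos (the targeted and empirical rates quoted in section 1.5.2.3 from the institution's earlier cohort, borrowed here as hospital rates);
- the 358 changes split 179 and 179;
- a share *f* of Jales changes falls back to empirical;
- procedures are independent, as the plan assumes.

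Targeted: T = 179(1 − f), at rate 0.064. Empirical: E = 179f from Jales plus 179 from Barretos, at rate

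p_E = (179f × 0.064 + 179 × 0.148) / (179f + 179).

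Crude OR = (0.064/0.936) / (p_E/(1 − p_E)). With f = 0 this is 0.0684/0.1737 = 0.39.

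Rejection probability = Φ((d − 1.96·SE0)/SE1), where d = p_E − 0.064, SE0 uses the pooled rate and SE1 the separate rates. With f = 0: SE0 = 0.0325, SE1 = 0.0322, d = 0.084, giving 0.735.

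| f | Targeted | Jales empirical | p_E | Crude OR | Share of hospital log-OR, ln(OR)/ln(0.3936) | Test rejects |
|---|---|---|---|---|---|---|
| 0% | 179 | 0 | 14.8% | 0.39 | 100% | 73.5% |
| 10% | 161 | 18 | 14.0% | 0.42 | 93% | 65% |
| 25% | 134 | 45 | 13.1% | 0.45 | 85% | 52% |
| 50% | 90 | 90 | 12.0% | 0.50 | 74% | 29% |

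With Jales supplying from 119 to 239 of the 358 changes and f from 0 to 50%, the share passed through runs from 59% to 100% and rejection from 24% to 73.5%. The nominal rate is 5%.

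**What a hospital term would leave.** If Barretos has only empirical changes, a hospital-adjusted estimate draws its information from Jales alone. The variance inflation from adding hospital is 1/(1 − φ²), with φ² = T·B/((E + B)·J), where J and B are the numbers of changes at Jales and Barretos and E is the Jales fallback number. At J = B = 179 it is 5.5, 2.5 or 1.5 for f = 10, 25 or 50%. At f = 0, φ² = 1 and the effect is not estimable.

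Power for 14.8% v 6.4% within Jales, by the same formula:

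| Jales changes | f = 10% | f = 25% | f = 50% |
|---|---|---|---|
| 119 | 25% | 33% | 32% |
| 179 | 31% | 43% | 45% |
| 239 | 37% | 52% | 56% |

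The crude 179 v 179 comparison has 73.5%. The smallest cells make the normal approximation rough (18 × 0.148 is fewer than 3 expected infections).

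**Direction within Jales.** Under section 4.10.3, a targeted change there is one where an agent was found; an empirical change is one that was untested or showed no specific agent. The contrast therefore also compares patients by culture result and by whether they were tested.

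**The case against.** A reader might infer that prophylaxis and hospital can never be separated and that any hospital difference passes one-for-one into the estimate. The fallback rule contradicts this: where it applies, Jales contributes to both groups. One-for-one transfer is the f = 0 limit.

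A reader might also infer that the groups come from different years. They do not: the windows share January 2014 to June 2020.

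Nor is every between-hospital difference left unadjusted. Neoplasm, performance status, metastases, degree of obstruction and resistance class are listed, and prior infection and bladder fistula are to be documented, so they could enter the regression. Section 4.12 also admits other characteristics of the procedures as candidates, Appendix II may list hospital, and the records come from two identified hospitals, so hospital is probably recoverable. Finally, section 4.10.3 says in general terms that prophylaxis type is read from records at both hospitals.

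These points limit the claim but do not remove it. The site-specific sentences still place targeted prophylaxis at Jales alone. Operators, culture-ordering habits and completeness of records are in neither list. Even if hospital is collected, nothing commits the analysis to using it, and a p < 0.20 screen could drop it. The crude tests adjust for nothing.

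**Conclusion.** The concern holds for catheter changes only. As written, the plan compares a Jales-only group with Barretos plus an unknown number of Jales fallback changes, and it specifies no hospital term or stratification. A significant difference could not be attributed to uroculture guidance. Under the assumptions above, a hospital difference alone gives a crude odds ratio of 0.39 to 0.50 and a false-positive rate of about 29% to 73.5% with equal hospital sizes, and 24% to 73.5% over the wider range of splits.

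The sizes depend on assumed hospital rates, hospital split and fallback share, none of which the documents give; the confounding itself follows from the text. The documents do not support saying that separation is impossible, that calendar time is a main driver, or that hospital was not collected. The one within-hospital contrast available under the protocol's definition is biased by culture status, so adding a hospital term is necessary but not sufficient.

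**What to change.** In the SAP, for catheter changes:

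1. Record hospital and procedure date for each procedure, and report the hospital-by-prophylaxis table before any model.
2. Keep hospital in the model whatever its univariate p-value.
3. Give hospital-specific estimates and a hospital-stratified (Mantel-Haenszel) estimate, noting where only Jales is informative.
4. Add a sensitivity analysis that classifies each change, in both hospitals, by whether a pre-change culture was taken to guide prophylaxis, whatever its result. State that this differs from the protocol's definition. It loosens the tie to the culture result and shows any overlap at Barretos.
5. Add a sensitivity analysis restricted to January 2014 to June 2020.
6. If overlap within a hospital is absent or too thin to estimate, state that the result compares two hospital policies and not prophylaxis types.

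The work is SAP wording, recoding from existing records and some extra tables. The real cost is precision: under the assumed splits, power for 14.8% v 6.4% falls from 73.5% crude to about 25% to 56% within Jales, and the adjusted effect is not estimable without overlap.
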